Table 6-3 shows the expected number of post-Day 29 infection events in the main study cohort overall and in the vaccinated group, as the assumed incidence absent vaccination varies. As shown, the design ensures a sufficient number of post-Day 29 infection events to address a variety of objectives that condition on post-Day 29 infection. For example, with 4% SARS-CoV-2 incidence absent vaccination, 75 post-Day 29 infection events are expected in the vaccinated group for immune correlates analyses.

Table 6-3 Expected number of post-Day 29 infection events, available for secondary analyses that condition on event status. Calculations assume 24,000 person-months of vaccinated follow-up and 24,000 person-months of unvaccinated follow-up and other assumptions in Table 6-2, $VE_S = 50\%$, and varying 16-week incidence of SARS-CoV-2 infection absent vaccination.

16-Week SARS-CoV-2 Background (unvaccinated) Incidence	Post-Day 29 Infection Events	
	Vaccinated and Unvaccinated Groups Combined	Vaccinated Group
1.5%	86	28
2%	143	47
3%	170	56
3.5%	198	66
4%	225	75

The study provides high power to evaluate the vaccine effect on acquisition (VE_S). Figure 6-1 shows the power of the study to detect a given level of VE_S , rejecting $H_0: VE_S \leq 30\%$, based on a 1-sided 0.025-level log-rank test and as a function of the SARS-CoV-2 incidence absent vaccination. With 4% 16-week incidence, the study has 90% power to detect any $VE_S > 57\%$; with 3% incidence, $VE_S > 60\%$ can be detected with 90% power.

The proposed study also provides adequate precision with which to estimate VE_S . Table 6-4 shows that, with 225 post-Day 29 infection events, the approximate 95% confidence interval (CI) about an estimated 50% VE_S is (36.9%, 60.4%). More precise inference is obtained under higher VE_S and higher post-Day 29 infection totals.

[figure not shown]

Figure 6-1 Power to detect varying vaccine efficacy (VE) against SARS-CoV-2 infection as a function of incidence absent vaccination over 16 weeks. Simulation-based power calculations assume 24,000 person-months of vaccinated and 24,000 person-months of unvaccinated follow-up and other assumptions listed in [Table 6-2](#). Power based on 1-sided 0.025-level log-rank test and 1,000 simulations.

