Table 6-4 Approximate 95% confidence interval around a given estimated VEs against SARS-CoV-2 infection, comparing vaccinated and unvaccinated groups as a function of the number of post-Day 29 infection events in the vaccinated and unvaccinated groups. Calculations assume 24,000 person-months of follow-up in each group and other assumptions in [Table 6-2](#).

Number of post-Day 29 infection events	Approximate 95% CI for estimated VE = 50%	Approximate 95% CI for estimated VE = 70%
200	(36.0%, 60.9%)	(60.7%, 77.2%)
225	(36.9%, 60.4%)	(61.1%, 76.9%)
250	(37.7%, 59.9%)	(61.6%, 76.6%)

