6.1.1 Power and precision for evaluating the vaccine effect on VL

Emerging data on acute SARS-CoV-2 infection suggest that with an expected 225 post-Day 29 infection events, the vaccine effect on mean peak \log_{10} viral load among post-Day 29 infection events can be estimated with adequate precision. Specifically, assuming that peak \log_{10} viral load is normally distributed with a 1.8 standard deviation in both treatment groups, and assuming 50% VEs, a 1-log reduction in mean peak viral load can be detected with 96.9% power given 225 post-Day 29 infection events; power remains high (93.5%) with 70% VEs. [Table 6-5](#) shows power to detect a 1-log reduction in peak \log_{10} viral load as a function of the assumed standard deviation in \log_{10} peak viral load which is allowed to vary between 1.0 and 2.5. The standard deviation in peak \log_{10} viral load in a cohort of

68 individuals associated with the National Basketball Association who were diagnosed with acute SARS-CoV-2 infection was 1.4 to 1.8, depending on the set of samples included in the analysis (50). Emerging data from the HCQ-PEP study of ~100 acutely infected household members of recently diagnosed COVID-19 cases suggests a standard deviation in peak log viral load in the range of 2.0-2.2, depending on the set of samples included [data not published]. [Table 6-6](#) shows the approximate 95% CI about an estimated 1-log reduction in mean peak log viral load, demonstrating the precision that is obtained with 225 post-Day 29 infection events. Modest precision is observed with a 1-1.8 standard deviation in the endpoint, with lower precision under a higher standard deviation; precision is also lower under increasing VEs.

Table 6-5 Power to detect a 1-log reduction in mean peak log viral load comparing post-Day 29 infection events between vaccinated and unvaccinated groups, as a function of the assumed standard deviation in peak log viral load in both groups and the assumed level of VE against SARS-CoV-2 infection. Simulation-based power calculations assume 225 post-Day 29 infection events across vaccinated and unvaccinated groups. Power based on 1-sided 0.025-level t-test and 1,000 simulations.

Std. dev. in peak log viral load	VE _S = 50%	VE _S = 70%
1	100%	100%
1.5	99.6%	97.8%
1.8	96.9%	93.5%
2	95.6%	86.5%
2.5	79.9%	68.7%

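### Protocol Table 6-4 and section 6.1 label 90% confidence intervals for VE_S as 95%, and the 2% row of Table 6-3 carries counts that fit 2.5% incidence

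*Protocol*

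**What the plan says.** Protocol 6.1 presents precision for VE_S as a design property. It states that "with 225 post-Day 29 infection events, the approximate 95% confidence interval (CI) about an estimated 50"% VE_S is (36.9%, 60.4%). Table 6-4 is headed "Approximate 95% confidence interval around a given estimated VEs against SARS-CoV-2 infection" and covers 200, 225 and 250 events at estimated VE 50% and 70%. On allocation it says: "Calculations assume 24,000 person-months of follow-up in each group and other assumptions in" Table 6-2. For the event split, 6.1 says that at 4% incidence and VE_S 50%, "75 post-Day 29 infection events are expected in the vaccinated group", out of 225.

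Table 6-3 ("Expected number of post-Day 29 infection events, available for secondary analyses that condition on event status") lists totals of 86, 143, 170, 198 and 225 against incidences of 1.5%, 2%, 3%, 3.5% and 4%.

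Protocol 6.1.1 gives 96.9% power to detect a 1-log reduction in peak viral load at VE_S 50% and SD 1.8 with 225 events, and adds that "power remains high (93.5%) with 70% VEs". The caption of Table 6-5 discloses that both columns assume 225 events. Table 6-7 gives median events of about 45 and 150 at VE_S 70%.

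**The concern.** The interval in the text looks too narrow for 225 events split 75 to 150. Table 6-4 is the only place where the protocol quantifies the precision of VE_S, and section 6.4.3.1 says that estimation matters more than testing for this endpoint. If the confidence level is mislabelled, a reader who compares achieved with planned precision uses too favourable a benchmark. The printed width at 225 events would need about 225 × (1.96/1.645)² ≈ 319 events at a true 95% level.

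Table 6-3 also breaks its own pattern. Successive totals rise by 57, 27, 28 and 27. The second step (2% to 3%) spans a full point of incidence, yet it rises by no more than the half-point steps that follow it, while the first half-point step rises by twice as much.

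**Working it through.** **Inputs.** 1:1 person-time (Table 6-4 caption); 225 events with 75 vaccinated at VE 50% (6.1); incidence, 10% baseline seropositivity, 98% per-protocol rate and 5% loss (Table 6-2); median events at VE_S 70% (Table 6-7). Both documents plan two-sided 95% inference: protocol 6.4.3.1 (type 1 error 0.05) and SAP 7.2 (95% Wald intervals).

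**1. Table 6-4.** With HR = 1 − VE and D events, vaccinated events are v = D·HR/(1+HR), unvaccinated events are u = D − v, SE = √(1/u + 1/v), and the limits for VE are 1 − HR·exp(±z·SE).

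At VE 50% and D = 225: SE = √(1/150 + 1/75) = 0.1414.
- z = 1.645: 1 − 0.5·exp(±0.2326) = (36.9%, 60.4%), exactly as printed.
- z = 1.960: 1 − 0.5·exp(±0.2772) = (34.0%, 62.1%).

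| VE | Events | SE | Printed as 95% | z = 1.645 | z = 1.960 |
|---|---|---|---|---|---|
| 50% | 200 | 0.1500 | 36.0, 60.9 | 36.0, 60.9 | 32.9, 62.7 |
| 50% | 225 | 0.1414 | 36.9, 60.4 | 36.9, 60.4 | 34.0, 62.1 |
| 50% | 250 | 0.1342 | 37.7, 59.9 | 37.7, 59.9 | 35.0, 61.6 |
| 70% | 200 | 0.1678 | 60.7, 77.2 | 60.5, 77.2 | 58.3, 78.4 |
| 70% | 225 | 0.1582 | 61.1, 76.9 | 61.1, 76.9 | 59.1, 78.0 |
| 70% | 250 | 0.1501 | 61.6, 76.6 | 61.6, 76.6 | 59.7, 77.6 |

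Eleven of twelve limits agree with z = 1.645. The exception is 60.7 against a computed 60.46; rounding does not explain it. The z implied by the printed widths is 1.62 to 1.65, a coverage of 89.5% to 90.1%. The log-scale width ratio is 1.645/1.960 = 0.84, hence 16% too narrow.

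**2. Is Table 6-4 an isolated slip?** Table 6-6 at SD 1.8 and VE 50%: 1 ± 1.96 × 1.8 × 0.1414 = (0.50, 1.50), as printed; z = 1.645 would give (0.58, 1.42). So the neighbouring precision table does use 95%.

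**3. Table 6-3.** Take 6,000 × 0.90 × 0.98 = 5,292 per arm, constant infection and loss hazards, VE_S 50%, and events in weeks 4 to 16.

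| Incidence | Computed total / vaccinated | Printed |
|---|---|---|
| 1.5% | 86 / 29 | 86 / 28 |
| 2% | 115 / 39 | 143 / 47 |
| 2.5% | 144 / 48 | no row |
| 3% | 173 / 58 | 170 / 56 |
| 3.5% | 202 / 68 | 198 / 66 |
| 4% | 230 / 77 | 225 / 75 |

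Scaling the printed rows linearly gives 225 × 2/4 = 112.5 to 86 × 2/1.5 = 114.7 at 2%, with 75 × 2/4 = 37.5 vaccinated. So about 114 and 38 belong at 2%, and 143 and 47 at 2.5%.

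**4. Power figures.** VE_S against a null of 30%: Φ(ln(0.70/0.43)/√(1/153 + 1/66.5) − 1.96) = 91.3% at 4% incidence and VE 57%; Φ(ln(0.70/0.40)/√(1/114.9 + 1/46.4) − 1.96) = 89.6% at 3% and VE 60%. Both agree with the stated 90%.

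Table 6-5, one-sided 0.025 t-test on 225 events, computed against printed at SD 1.8, 2 and 2.5:
- VE 50%: 97.4, 94.1, 80.4 against 96.9, 95.6, 79.9.
- VE 70%: 93.8, 88.2, 71.1 against 93.5, 86.5, 68.7.

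All ten cells, including SD 1 and 1.5, lie within 2.4 points. In only one does the printed value exceed the computed one appreciably: 95.6 against 94.1, about two Monte Carlo standard errors for 1,000 simulations.

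**5. Event total at VE 70%.** Table 6-7 implies 45 + 150 = 195. The t-test with that split gives 90.2% at SD 1.8 and 64.9% at SD 2.5, against 93.5% and 68.7% printed for 225.

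**The case against.** *Another variance formula might rescue the 95% label.* With SE = 2/√D and z = 1.96, the VE 70% column comes out at (60.4, 77.3), (61.0, 76.9) and (61.6, 76.6), about as close to print as the 90% reading. This stands for that column alone. At VE 50% and 225 events the same formula gives (35.1, 61.5), not (36.9, 60.4). An exact conditional interval at 95% gives (33.6, 62.6). Only the 90% level fits the whole table.

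*The Table 6-3 row may be a label error.* This stands. A 2.5% could have been printed, or extracted, as 2%. A reader might infer that the plan promises about a quarter more events than 2% incidence would yield (143/115 = 1.24), but that holds only if the label is right and the counts are wrong. The documents do not settle which, and the text of 6.1 draws no conclusion from this row.

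*A reader might also infer that the stated power is overstated.* The documents do not support that. The VE_S power figures reproduce at one-sided 0.025, and Table 6-5 reproduces on its disclosed 225 events. Replacing 225 by 195 changes the scenario; it does not expose a miscalculation.

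*The consequence is small.* This also stands. The corrected lower limits at VE 50% (32.9%, 34.0%, 35.0%) all remain above 30%. The criterion in 6.4.3.1, a lower limit above 30% under VE above 60%, rests on the power calculation. SAP 2.5 does not repeat the Table 6-4 intervals, and it says that the trial, stopped early, is underpowered for its primary objectives.

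**Conclusion.** Table 6-4 and the matching sentence in 6.1 are wrong as written: they report 90% intervals as 95%. At 225 events and VE 50% the lower limit is 34.0%, not 36.9%, so the margin above 30% is 4.0 points instead of 6.9. This rests on the usual large-sample variance of the log hazard ratio with equal person-time, which reproduces all but one printed limit at z = 1.645.

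The 2% row of Table 6-3 is inconsistent with Table 6-2 and with the other four rows; whether the label or the counts are at fault cannot be determined.

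The power statements stand. One consistency note remains: 6.1.1 calls 225 events expected, but that is the expectation at VE_S 50% and 4% incidence. At VE_S 70% the design expects about 195, and the viral-load power is then about 90% at SD 1.8 and 65% at SD 2.5.

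These are corrections to planning text. They matter for the public record of intended precision and alter no inference.

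**What to change.** - **Table 6-4 and the sentence in 6.1:** replace the limits with the z = 1.960 column above, or keep them and relabel as 90%. Printing 95% values is preferable because the planned analysis and Table 6-6 use that level. If the table is kept as 90%, check the 60.7% entry.
- **Table 6-3:** check the source calculation, then either relabel the row 2.5% or restate it as about 114 total and 38 vaccinated.
- **Section 6.1.1 (optional):** add a sentence that the VE_S 70% columns of Tables 6-5 and 6-6 are conditional on 225 events, that about 195 are expected there, and that power is then about 90.2% at SD 1.8 and 65% at SD 2.5.

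The cost is six intervals, one sentence and one table row, with slightly less favourable precision on paper. Sample size, tests and analyses are unaffected.

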6.1.1 Power and precision for evaluating the vaccine effect on VL

Emerging data on acute SARS-CoV-2 infection suggest that with an expected 225 post-Day 29 infection events, the vaccine effect on mean peak \log_{10} viral load among post-Day 29 infection events can be estimated with adequate precision. Specifically, assuming that peak \log_{10} viral load is normally distributed with a 1.8 standard deviation in both treatment groups, and assuming 50% VEs, a 1-log reduction in mean peak viral load can be detected with 96.9% power given 225 post-Day 29 infection events; power remains high (93.5%) with 70% VEs. [Table 6-5](#) shows power to detect a 1-log reduction in peak \log_{10} viral load as a function of the assumed standard deviation in \log_{10} peak viral load which is allowed to vary between 1.0 and 2.5. The standard deviation in peak \log_{10} viral load in a cohort of

68 individuals associated with the National Basketball Association who were diagnosed with acute SARS-CoV-2 infection was 1.4 to 1.8, depending on the set of samples included in the analysis (50). Emerging data from the HCQ-PEP study of ~100 acutely infected household members of recently diagnosed COVID-19 cases suggests a standard deviation in peak log viral load in the range of 2.0-2.2, depending on the set of samples included [data not published]. [Table 6-6](#) shows the approximate 95% CI about an estimated 1-log reduction in mean peak log viral load, demonstrating the precision that is obtained with 225 post-Day 29 infection events. Modest precision is observed with a 1-1.8 standard deviation in the endpoint, with lower precision under a higher standard deviation; precision is also lower under increasing VEs.

Table 6-5 Power to detect a 1-log reduction in mean peak log viral load comparing post-Day 29 infection events between vaccinated and unvaccinated groups, as a function of the assumed standard deviation in peak log viral load in both groups and the assumed level of VE against SARS-CoV-2 infection. Simulation-based power calculations assume 225 post-Day 29 infection events across vaccinated and unvaccinated groups. Power based on 1-sided 0.025-level t-test and 1,000 simulations.

Std. dev. in peak log viral load	VE _S = 50%	VE _S = 70%
1	100%	100%
1.5	99.6%	97.8%
1.8	96.9%	93.5%
2	95.6%	86.5%
2.5	79.9%	68.7%

Table 6-6 Approximate 95% confidence interval around an estimated 1-log reduction in mean peak log viral load comparing post-Day 29 infection events between vaccinated and unvaccinated groups, as a function of the assumed standard deviation in peak log viral load in both groups and the assumed level of vaccine efficacy against SARS-CoV-2 infection. Calculations assume 225 post-Day 29 infection events across vaccinated and unvaccinated groups.

Std. dev. in peak log viral load	VE _S = 50%	VE _S = 70%
1	(0.72, 1.28)	(0.68, 1.31)
1.5	(0.57, 1.41)	(0.51, 1.46)
1.8	(0.50, 1.50)	(0.44, 1.57)
2	(0.46, 1.57)	(0.36, 1.61)
2.5	(0.29, 1.65)	(0.20, 1.74)

6.1.2 Power for evaluating the vaccine effect on secondary transmission

The study has adequate power to evaluate vaccine efficacy against secondary transmission, based on analyses that are conducted among post-Day 29 infection events in the Main study cohort and their contacts in the PCC and CACC, ie, based on conditional analyses, as long as VE against SARS-CoV-2 infection is low. As demonstrated in [Figure 6-2](#), if there is high vaccine efficacy against

SARS-CoV-2 infection, power is low to evaluate secondary transmission using a conditional analysis. In this case, an unconditional analysis of VE against secondary transmission is planned and is expected to be more powerful, and also more appropriate given that it reflects that infections blocked have no transmission potential.

We performed simulation-based calculations to explore the power to evaluate VE against secondary transmission based on a conditional analysis that compares secondary transmission events among contacts of vaccinated and unvaccinated main study participants. In addition to the assumptions in [Table 6-2](#), we assumed: equal infection surveillance in the PCC and CACC; that PCC contacts acquire infection from outside sources (other than the index case) at the same rate as the Standard of Care Group; that only baseline seronegative contacts and those in the PCC not infected by outside sources are at risk of secondary transmission; that the number of secondary transmission events among at-risk contacts follows a Poisson distribution in each arm, with VE against secondary transmission reducing the event rate proportionally given vaccination. A one-sided 0.025-level likelihood ratio test based on a Poisson regression model was used to evaluate VE against secondary transmission. As shown in [Figure 6-2](#), the study has 90% power to detect a 59% reduction in secondary transmission if $VE_S = 50\%$; a higher 69% reduction in secondary transmission is detectable if $VE_S = 70\%$. [Table 6-7](#) helps explain the power results: it shows the amount of statistical information on which the analysis is based, ie, the median number of post-Day 29 infection events and associated secondary transmission events in the vaccinated and unvaccinated groups. With 50% VE_S and 50% VE against secondary transmission, we expect 15 secondary transmission events in the vaccinated group and 59 in the unvaccinated group; the limited number of events is due to the “transmission cascade” whereby under our assumptions only some SARS-CoV-2 infected participants enroll contacts into the PCC and CACC, only some contacts are susceptible and retained, and the transmission rate is low (15%).

[figure not shown]

Figure 6-2 Power to detect varying vaccine efficacy against secondary transmission as a function of vaccine efficacy against SARS-CoV-2 infection. Simulation-based power calculations assume 24,000 person-months of vaccinated follow-up and 24,000 person-months of unvaccinated follow-up and other assumptions listed in **Table 6-2**. Power based on 1-sided 0.025-level likelihood ratio test under Poisson regression model and 1,000 simulations.

Table 6-7 Number of post-Day 29 infection events and associated secondary transmission events in the vaccinated and unvaccinated groups, under varying VE against SARS-CoV-2 infection and varying VE against secondary transmission, under other assumptions laid out in Table 6-2, and based on 1,000 simulations.

VE against secondary transmission	VEs = 50%		VEs = 70%	
	Median no. post-Day 29 infection events, Vaccinated vs. Unvaccinated Groups (IQR)	Median no. secondary transmissions, Vaccinated vs. Unvaccinated Groups (IQR)	Median no. post-Day 29 infection events, Vaccinated vs. Unvaccinated Groups (IQR)	Median no. secondary transmissions, Vaccinated vs. Unvaccinated Groups (IQR)
VE = 0%	76 (70-82) vs. 150 (142-158)	29 (25-34) vs. 59 (53-66)	45 (41-50) vs. 149 (141-158)	18 (14-21) vs. 59 (53-65)
VE = 40%	76 (70-81) vs. 150 (142-158)	18 (15-21) vs. 59 (53-64)	45 (41-50) vs. 149 (142-158)	11 (8-13) vs. 59 (53-65)
VE = 50%	76 (70-82) vs. 150 (143-159)	15 (12-17) vs. 59 (53-66)	45 (41-50) vs. 150 (142-158)	9 (7-11) vs. 59 (53-65)
VE = 60%	76 (70-82) vs. 150 (142-158)	12 (9-14) vs. 58 (52-65)	45 (41-50) vs. 151 (143-159)	7 (5-9) vs. 59 (53-65)
VE = 70%	75 (70-81) vs. 150 (142-158)	9 (7-11) vs. 58 (52-65)	46 (41-50) vs. 150 (142-159)	5 (4-7) vs. 59 (53-65)

6.2 Role of the Independent Data Monitoring Committee (IDMC)

The study IDMC will provide study oversight and ensure that the study is on-target to meeting its objectives in a timely fashion. The IDMC will receive summaries of study progress throughout the study. Given the short duration of the study and the considerable prior data establishing safety and efficacy of the

vaccine, and the status of the EUA vaccine, there will be no pre-specified interim monitoring boundaries for VE or non-efficacy. The IDMC will make recommendations to protocol chairs and lead advisors. The set of metrics, operational targets for them, and potential remedial actions will be laid out in full in the IDMC Charter.

6.3 Randomization

A participant's randomization assignment will be computer generated and provided to the CRS study staff through a Web-based randomization system.

Randomization will be stratified. The randomization will be done in blocks to ensure balance among contemporaneously evaluated Immediate Vaccination and Standard of Care arms within levels defined by study site and type of residence.

6.4 Statistical analyses

This section describes the final study analyses which will occur after the last main study participant has completed the Month 4 visit. All data from enrolled participants will be analyzed according to the initial group assignment regardless of how and when in-study and outside-study vaccinations are received. Follow-up and endpoints that accrue post-outside-study-vaccination will be censored for primary and secondary analyses. In the rare instance that a participant receives study vaccination at the wrong time, the Statistical Analysis Plan (SAP) will address how to analyze the data. Analyses are modified intent-to-treat in that individuals who are randomized but not enrolled do not contribute data and hence are excluded. Because of the brief length of time between randomization and enrollment, few such individuals are expected.

The SAP will specify how data from the Vaccine Declined group will contribute to assessing primary and secondary objectives. Wherever possible, analyses will limit to data collected on randomized participants, and will entail comparing outcomes between those randomized to Immediate Vaccination or Standard of Care. However, if operational data on enrollment, retention, adherence to study procedures suggest that there will be insufficient unvaccinated follow-up for the Standard of Care Group to permit a specific analysis, data from the Standard of Care Group will be combined with data from the Vaccine Declined Group, with methods fully pre-specified in the SAP.

Analyses for primary endpoints will be performed using SAS and R. All other descriptive and inferential statistical analyses will be performed using SAS, StatXact, or R statistical software.

In general, no formal multiple comparison adjustments will be employed for multiple secondary endpoints. However, multiplicity adjustments will be made for

certain immunogenicity assays, as discussed below, when the assay endpoint is viewed as a collection of hypotheses (eg, testing multiple peptide pools to determine a positive response).

